7.1 Study Procedures/Evaluations

Once enrolled, participants will be asked to undergo physical examination (as standard of care), questionnaires facilitated by study staff, blood draws and collection of urine and stool samples.

7.1.1 Study Specific Procedures

- **Medical history** will be obtained by interview at screening and/or medical records
- **Medication history** will be obtained by interview and/or medical records. Assessment of eligibility will include a review of permitted and prohibited medications.
- **Physical examination** including assessments of tender and swollen joint counts will be performed by the physician and/or study staff at each clinic visit and recorded.
- **Biological specimen collection and laboratory evaluations** will be collected as above. Briefly,
 - Stool and urine will be collected by participant at home or in clinic per participant preference. Each participant will be given a stool/urine collecting kit along with detailed instructions on how to handle, store, and send specimen (should collection be at home) to the [name] research laboratory at the NYU Langone Orthopedic Hospital. Samples will be aliquoted into collection

tubes and stored at -80C until used for SCFA quantification, genomic, metabolomics and/or transcriptomic analyses.

- Urine will be collected from participants in sterile containers. Urine will be stored and analyzed at a later time point for potential biomarkers, metabolic breakdown products of methotrexate and stored for analyses related to this study.
- Blood samples will be collected as above for measurements of inflammation, immune activation, RNA transcripts and/or genomics.
- **Assessment of study agent adherence** will be performed at each clinic visit with quantification of remaining SCFA oral supplements given to the participant and with occasional phone calls reviewing compliance. Participants not taking oral SCFA supplements will not be assessed on study agent adherence.
- **Administration of questionnaires** DAS28 and MDHAQ will be performed at clinic visits by the study staff.

7.1.2 Standard of Care Study Procedures

Detailed physical exam including assessment of tender and swollen joint count will be completed at each clinic visit as part of regular standard of clinical care. Blood draws to look for markers of inflammation will also be completed as part of regular standard of clinical care. Treating physician will have discretion to make changes to methotrexate dosage at his/her discretion. If participant is switched to a new medication and methotrexate is discontinued, participant will no longer be eligible to continue in the study.

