3.2 Secondary Objectives (if applicable)

- To determine whether oral SCFA supplementation in RA inadequate responders induces changes in the peripheral Treg population
- To measure changes in adaptive immune response over time with oral supplementation of SCFA
- To measure changes in serum and fecal SCFA concentration with oral supplementation of SCFA
- To measure MTX and its metabolites in fecal and urine samples after oral SCFA supplementation

4 Study Design and Endpoints

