4.1 Description of Study Design

This study is a pilot proof of concept, open label study of the effects of oral SCFA supplementation in RA patients with an inadequate response to MTX. We will be enrolling all patients with RA who fulfill inclusion/exclusion criteria. This will be a single center study based in the NYU Langone hospitals and clinics as well as Bellevue Hospital which falls under its umbrella. Oral butyrate will be taken at 1000 mg three times daily with meals by RA patients who have active disease and are currently taking MTX at prescriber's recommended dose. There will be no dose escalation of the study supplement.

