5.1 Inclusion Criteria

In order to be eligible to participate in this study, an individual must meet all of the following criteria:

1. Diagnosis of RA meeting 2010 ACR/EULAR for RA and/or treating MD diagnosis
2. Inadequate response to MTX per treating MD at maximum tolerated dose.
3. Able and willing to provide written informed consent prior to any study specific procedures
4. Age 18 years and above at time of enrollment
5. Subjects not excluded based on race or ethnicity

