7.2.2 Specimen Shipment

If stool sample is NOT collected on day of visit (either day 0, month 1, month 2), participant can opt to collect specimen at home in a collection kit that we provide, and ship, on provided ice packs to

[name]/[name] MiCRA Lab
NYU Hospital for Joint Diseases
[name]
[name]

Specimens can be shipped Monday, Tuesday, or Wednesday with a shipping label that we provide.

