7.3 Study Schedule

	Screening/Baseline	Month 1	Month 2*	Month 12*
Visit #	1	2	3*	4*
Day#	- 15 to 0	30±15	60±15	61 to 421
Informed consent	X			
Medical history	X			
Medications	X	X	X	X
MDHAQ Questionnaire	X	X	X	X
TJ/SJ counts	X	X	X	X
DAS28	X	X	X	X
Blood collection	X	X	X	X
Stool/urine sample	X	X	X	X
Dispense SCFA	X	X*		
Adverse events	X	X	X	X

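### The methotrexate-metabolite objective has no endpoint or analysis, and its stool and urine samples are not linked to MTX dose, route or time since last dose

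*Combined protocol and SAP*

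**What the plan says.** The Protocol Summary places this among the key secondary objectives, and section 3.2 repeats it: "To measure MTX and its metabolites in fecal and urine samples after oral SCFA supplementation". Section 7.1.1 adds for urine: "Urine will be stored and analyzed at a later time point for potential biomarkers, metabolic breakdown products of methotrexate". Section 4.2.2 has no matching endpoint. Sections 9.1 and 9.2 give no analysis for it, and section 9.1 says there will be no formal SAP.

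On the drug being measured:

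- Section 5.1 requires "Inadequate response to MTX per treating MD at maximum tolerated dose", and section 4.1 describes patients who "are currently taking MTX at prescriber's recommended dose". No route, dosing day, dosing interval or stable-dose period is stated.
- Section 7.1.2 says "Treating physician will have discretion to make changes to methotrexate dosage at his/her discretion" and continues: "If participant is switched to a new medication and methotrexate is discontinued, participant will no longer be eligible to continue in the study".

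On sampling:

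- The schedule in section 7.3 has "Stool/urine sample" at every visit, with visit 1 on Days -15 to 0 and visit 2 on Day 30 ± 15.
- Collection is at home or in clinic as the participant prefers (section 7.1.1). For home samples, "Specimens can be shipped Monday, Tuesday, or Wednesday with a shipping label that we provide" (section 7.2.2).
- Medications are reviewed at each visit (section 7.3) and recorded on case report forms (section 7.4). The protocol does not specify fields for MTX dose, route or time of last dose. The adherence check in section 7.1.1 covers SCFA capsules only.

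**The concern.** What is found in stool or urine depends on how much MTX was taken, by what route and how long ago. The protocol leaves all three free to vary between visits and does not ask for them to be recorded with the sample. No concurrent group on the same MTX treatment is assigned to this objective: the control group is non-randomised, proceeds to next-line therapy, and is given a different role in section 9.1. With no endpoint or analysis defined either, a difference between visits 1 and 2 would be hard to interpret. Time since last dose is much easier to capture at collection than to reconstruct from stored samples.

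**Working it through.** **1. The plan's own figures.** There is none for this objective. The sample size concerns Shannon diversity and reproduces. For a two-sided Wilcoxon signed-rank test at 0.05, 23 participants give 80.4% power at d = 0.63, and 25 give 80.1% at d = 0.60 (noncentral t with efficiency 3/π, confirmed by simulation). Only n = 25 is carried forward.

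**2. Calendar.** Assume weekly MTX. Visit 2 covers Days 15 to 45, which is 31 days. With visit 1 on Day 0, the days at the same point of the MTX week are 21, 28, 35 and 42: 4/31 = 12.9%. Over all 16 possible visit 1 days, ten leave 4 matching days and six leave 5: (10 × 4 + 6 × 5)/(16 × 31) = 70/496 = 14.1%. This treats all days as equally likely and is essentially 1 in 7. It also shows that at least 4 matching days always exist inside the visit 2 window.

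**3. Precision.** Assume log-linear decay with half-life h, time since dose uniform over 168 h and independent at each visit, residual SD of the visit 2 to visit 1 log-ratio 0.50, n = 25 and a true log-ratio of 0.30. Then

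Var = 0.50² + 2 × (ln 2/h)² × 168²/12.

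- h = 72: 0.25 + 1.617²/6 = 0.686
- h = 48: 0.25 + 2.426²/6 = 1.231
- h = 24: 0.25 + 4.852²/6 = 4.174

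The error rates below come from 6,000 simulated trials per row.

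| Sampling time | SD | 0.30/SD | False positives, no effect | Power |
|---|---|---|---|---|
| Fixed | 0.50 | 0.60 | 5% | 80% |
| Random, h = 72 h | 0.83 | 0.36 | 4% | 39% |
| Random, h = 48 h | 1.11 | 0.27 | 5% | 23% |
| Random, h = 24 h | 2.04 | 0.15 | 4% | 10% |

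The false-positive rate does not rise. The cost is power.

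**4. Bias from dose changes.** Assume levels proportional to dose, no SCFA effect, and a fraction p of participants whose dose is multiplied by f between visits, with the change ignored. The mean log-ratio shifts by p × ln f. Reductions by the same factor give the same rates, because the test is two-sided and symmetric on the log scale.

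| p, f | Shift | False positives: fixed time, SD 0.50 | Fixed time, SD 0.30 | Random time, h = 48 h, SD 0.50 |
|---|---|---|---|---|
| 20%, 1.25 | 0.045 | 7% | 10% | 5% |
| 20%, 1.5 | 0.081 | 11% | 18% | 6% |
| 40%, 1.25 | 0.089 | 12% | 26% | 7% |
| 40%, 1.5 | 0.162 | 27% | 55% | 9% |

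With p = 10% the fixed-time rate at SD 0.50 is 5-6%. With increases and decreases balanced (20% each, f = 1.5) it stays at 5%. Where sampling time is also random, its noise masks much of the bias.

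**The case against.** A reader might infer that sampling day and MTX dose changes will be reported as an SCFA effect. The documents do not support that. No analysis is specified, so nothing says how a difference would be read. Unsystematic variation in time since dose leaves the false-positive rate at 4-5%. Dose changes bias the result only if they lean one way and are ignored. The shipping rule applies at every visit, so it gives no evident reason for a systematic shift.

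Other points on that side also have weight:

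- The objective speaks of measuring after supplementation. A visit 1 to visit 2 comparison is inferred, though samples are taken at both visits and the word after needs a reference.
- Entry at maximum tolerated dose limits later increases, and a switch that stops MTX ends participation. Dose reductions, however, remain possible.
- The case report form and kit instructions are not in the documents. One can say only that the protocol does not specify the fields, not that they are absent.
- Samples carry a collection date (section 5.5.2). With weekly dosing, a participant's usual dosing day would give approximate days since dose, so the information is not wholly lost.
- If both samples are shipped from home on the day of collection, and the three shipping days are equally likely, the weekday matches in 3/9 = 33% of pairs, not 14%.
- Very large fold differences between sampling days follow only from short assumed half-lives. Over 3 days the ratio is 2^(72/24) = 8 at 24 h but 2^(72/72) = 2 at 72 h, and no document supports one decay curve for stool, urine and every metabolite.

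These points limit the claim. They do not supply an endpoint, an analysis or a requirement to record dose, route and last-dose time with each sample.

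**Conclusion.** The point holds as a gap in one secondary objective: no endpoint, no analysis, and no link between the samples and MTX dose, route or time since dose, while the dose may change between visits. The main consequence is imprecision (illustrative power falling from 80% to about 10-39%). The second is possible confounding by one-directional, unadjusted dose changes (illustrative false-positive rate about 7-27% at fixed sampling time, and about 5-9% when time since dose also varies at random with a 48 h half-life). An observed change could not be clearly separated from an SCFA effect.

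Weekly dosing, the half-lives, the SDs, the size of the effect and the dose-change rates are all assumptions, so these figures show direction and rough scale only. If MTX is not taken weekly, steps 2 and 3 do not apply as they stand. The primary endpoint and its n = 25 are not affected.

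**What to change.** 1. With every stool and urine sample, at home or in clinic, record the MTX dose, route, date and time of the last MTX dose, and the collection date and time.
2. Define the endpoint in section 4.2.2 as the within-participant change from visit 1 to visit 2 in MTX and metabolite levels, in participants taking SCFA.
3. State the analysis in section 9.1: the change in level (for example the log-ratio), adjusted for MTX dose and time since dose at each visit, with a sensitivity analysis in participants whose dose and route did not change. State that it remains an uncontrolled before-after comparison.
4. Where practical, ask participants to collect both samples a similar number of days after their MTX dose. Count from each participant's actual visit 1 collection rather than naming fixed study days: Days 28 and 35 match only if visit 1 fell on Day 0, -7 or -14. Keep collection inside the existing visit 2 window, because the same stool supplies the primary endpoint.

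The cost is a few form fields, a short analysis paragraph and slightly less flexible collection. The sensitivity analysis will use fewer than the full set of participants. MTX care, the primary endpoint and the sample size stay as they are.

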CRF	Case Report Form
CSOC	Clinical Study Oversight Committee
DCC	Data Coordinating Center
DHHS	Department of Health and Human Services
DSMB	Data and Safety Monitoring Board
FFR	Federal Financial Report
FWA	Federalwide Assurance
GCP	Good Clinical Practice
HIPAA	Health Insurance Portability and Accountability Act
ICF	Informed Consent Form
ICH	International Conference on Harmonisation
IR	Inadequate responder
IRB	Institutional Review Board
ISM	Independent Safety Monitor
MOP	Manual of Procedures
MTX	Methotrexate
N	Number (typically refers to participants)
NIH	National Institutes of Health
OHRP	Office for Human Research Protections
OHSR	Office of Human Subjects Research
PI	Principal Investigator
QA	Quality Assurance
QC	Quality Control
RA	Rheumatoid arthritis
SAE	Serious Adverse Event/Serious Adverse Experience
SOP	Standard Operating Procedure
US	United States

[figure not shown]
Protocol Summary

Title	A pilot proof of concept study of the E ffects of A Administration of S CFAs in R heumatoid A rthritis I nadequate R esponders
Short Title	EASi-RAIR
Brief Summary	
This study is a pilot, proof of concept study to determine the effects of administering an oral SCFA supplement to RA patients with inadequate response to methotrexate. We will include up to 65 total participants to obtain the following sample sizes below. We will include up to 65 participants to obtain a sample size of at least 25 participants taking the oral supplement. We hypothesize that oral SCFA will change the participants' gut microbiome and regulatory immune responses. Additionally, we will include participants with inadequate response to methotrexate who do not want to take oral SCFA supplements but rather proceed directly to the next medication their treating physician suggests. We will include up to 30 participants to obtain a sample size of at least 20 participants. Clinical data to assess for adverse events, stool, urine samples and peripheral blood will be collected at baseline, 1 month, with an optional 2-month time-point, and an optional visit up to 12-months following the last visit after participants have started treatments with the next line of therapy. Fecal microbiome will be analyzed. Adaptive immune responses will be analyzed from participant blood samples.

Phase	Pilot proof of concept study

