Objectives	
Primary objective:
 
 To determine whether oral SCFA supplementation in RA inadequate responders induces changes in the gut microbiome composition 
Key secondary objectives:
 
 To determine whether oral SCFA supplementation in RA inadequate responders induces changes in the peripheral Treg population To measure changes in adaptive immune response over time with oral supplementation of SCFA To measure changes in serum and fecal SCFA concentration with oral supplementation of SCFA To measure MTX and its metabolites in fecal and urine samples after oral SCFA supplementation To measure changes in the gut microbiome composition in methotrexate inadequate responders who do not want to take oral SCFA supplements. To measure changes in the gut microbiome composition in methotrexate inadequate responders after they initiate next line therapy (as prescribed by their treating physician)
Methodology	Open label pilot proof of concept study
Endpoint	
Primary endpoint:
 
 The primary endpoint will be an increase in microbiome alpha diversity from baseline visit 1 to visit 2 after SCFA supplementation. 
Important secondary endpoints:
 
 We will determine the changes to serum and fecal SCFA after SCFA supplementation and determine the changes in adaptive immune response including peripheral Treg cell populations.
Study Duration	Up to 4 years
Participant Duration	Up to 14 months

[figure not shown]
Duration of IP administration	Up to 2 months
Population	Any Rheumatoid Arthritis patient who is an inadequate responder to current RA treatment: 
• Age 18 years and above• Subjects not excluded based on gender, race or ethnicity, general health status, or geographic location
Study Sites	NYU Langone Health inpatient and outpatient sites, Bellevue Hospital
Number of participants	65 participants
Description of Study Agent/Procedure	Study agent is an oral SCFA supplement containing butyrate. It will be taken orally 1000mg three times a day with meals.
Key Procedures	Blood draws Stool collection Urine collection

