5.4 Strategies for Recruitment and Retention

Recruitment

Potential subjects will be informed of the study by their treating physicians. Treating physicians will be informed of the study verbally. Additionally, individuals with inadequate response to methotrexate who do not want to take oral SCFA supplements but rather proceed directly to the next medication their treating physician suggests; are also considered potential subjects, serving as the control group, and will be informed of the study by their treating physician. If patients agree to be contacted for participation, a member of the study team will approach them in person, by phone, via MyChart message. These recruitment materials are uploaded in Research Navigator. The study team also welcomes potential subjects from outside NYULH or Bellevue Hospital who may learn about the study from clinicaltrials.gov or by word-of-mouth.

Once contact is made, subjects will be told the reason they are being contacted and asked if they are interested in participating in this specific study. If the potential subjects agree, the study team will provide them with information regarding the next steps for participation.

If a subject requests information regarding opting out of further recruitment for all research, subjects will be directed to contact study coordinator or have subjects contact [contact] or [name].

Sex of Subjects

Both men and women will be equally recruited into the study. Since RA affects women over men by approximately 3-fold, we will likely recruit more women due to the epidemiology of this disease. There are no enrollment restrictions regarding gender of subject.

Age of Subjects.

Age of the enrolled subjects will be at least 18 years of age.

Racial and Ethnic Origin.

All racial and ethnic groups will be recruited into the study, without any restrictions.

Subject capacity:

Subjects with impaired cognitive capacity will not be consented or enrolled into the study.

Subject comprehension:

If any questions arise, the Study Staff will answer them until the subject has a clear understanding of what is expected if he/she agrees to participate in the study. Each subject will be asked to provide a statement of understanding of the study risks, procedures and what the study entails prior to signing the Study Informed Consent.

Documentation of consent:

Original documents of the Study Informed Consent will be maintained for study purposes and review, if needed.

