5.9 Premature Termination or Suspension of Study

This study may be temporarily suspended or prematurely terminated if there is sufficient reasonable cause. Written notification, documenting the reason for study suspension or termination, will be provided by the suspending or terminating party to [name], the funding agencies, and regulatory authorities. If the study is prematurely terminated or suspended, the PI will promptly inform the NYU IRB and will provide the reason(s) for the termination or suspension.

Circumstances that may warrant termination or suspension include, but are not limited to:

- Determination of unexpected, significant, or unacceptable risk to participants
- Demonstration of efficacy that would warrant stopping
- Insufficient compliance to protocol requirements
- Data that are not sufficiently complete and/or evaluable
- Determination of futility

Study may resume once concerns about safety, protocol compliance, data quality are addressed and satisfy the sponsor and/or the NYU IRB.

Patients who are discontinued from study compound for any reason other than an SAE will be encouraged to remain on the study (not be officially withdrawn from the study) and complete all study visits. The data obtained will be used to understand variations in microbiome and Treg after discontinuation of SCFA.

6 Study Agent (Study drug, device, biologic, vaccine etc.) and/or Procedural Intervention

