9.1 Statistical and Analytical Plans (SAP)

The primary endpoint will be an increase in microbiome diversity (as measured by Shannon diversity index) from baseline visit 1 to visit 2 after SCFA supplementation with an effect size of at least 0.60. Our preliminary data of NORA patients reveals an increase in alpha diversity after butyrate supplementation with an effect size of 0.63 (Cohen's d) (unpublished data). Using this effect size for a two-tailed Wilcoxon signed-rank test, to be powered at 80% with a 0.05 type I error rate, we would need 23 participants to see a difference in pre-post treatment response in alpha diversity. However, to be more conservative, we will aim for 25 participants in order to achieve an effect size of at least 0.6 while maintaining 80% power with a 0.05 type I error. This number of participants is in line with previous studies^{11,21} and therefore should be sufficient for ours. These estimated sample sizes are based on before and after differences of the study group and we will not include a placebo group for the current proof-of-principle study. There will not be a formal SAP because due to the pilot nature of the proof of principle study.

Addition of a control group that do not take the SCFA supplement will not change the statistical analysis of the primary endpoint above since in the primary endpoint, the participants taking the SCFA supplement act as their

own controls. The additional control group will be used to explore secondary endpoints such as if there are gut microbial shifts after starting next line therapy as proposed by their treating physician.

It is expected that approximately 65 participants will be enrolled to produce at least 25 evaluable participants.

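### Section 7.1.2 ends participation when a new drug replaces methotrexate, so next-line microbiome data would come only from participants who stay on methotrexate

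*Combined protocol and SAP*

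**What the plan says.** Section 7.1.2 leaves methotrexate (MTX) dosing to the treating physician and then sets a removal rule: "If participant is switched to a new medication and methotrexate is discontinued, participant will no longer be eligible to continue in the study". The rule is written for any participant, without limit by group or visit.

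Four other places describe people whom the study intends to follow onto a new drug:

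- **Control-group definition** (Section 5.4; the Brief Summary is to the same effect): MTX inadequate responders "who do not want to take oral SCFA supplements but rather proceed directly to the next medication their treating physician suggests".
- **Key secondary objective** (Protocol Summary, Objectives): "To measure changes in the gut microbiome composition in methotrexate inadequate responders after they initiate next line therapy (as prescribed by their treating physician".
- **Use of the control group** (Section 9.1): secondary questions such as "if there are gut microbial shifts after starting next line therapy as proposed by their treating physician".
- **Late visit** (Brief Summary): "an optional visit up to 12-months following the last visit after participants have started treatments with the next line of therapy". The schedule in Section 7.3 places it at Days 61 to 421 and marks it optional.

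Section 7.3.5 asks for a final stool, urine and blood sample at withdrawal or early termination if the participant is willing. Section 6.1.9 defines an evaluable participant only by two weeks of supplementation.

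**The concern.** For a participant whose next drug replaces MTX, the exposure named in the secondary objective is the same event that ends participation. Followed literally, the protocol has staff stop observing people whom a stated objective needs them to observe. Add-on patients would supply the next-line results, which could then be read as describing everyone who moved to next-line therapy.

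The same rule can remove an SCFA participant before Visit 2, where the primary endpoint is measured. No text says how such a person enters the primary analysis. That analysis is an uncontrolled before-after comparison, so no concurrent group would reveal a selection effect.

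**Working it through.** **1. The plan's own figure.** Sections 9.1 and 9.2 give 23 participants at d = 0.63 and 25 at d = 0.60 (two-sided Wilcoxon signed-rank test, 80% power, alpha 0.05). I used noncentral-t power with effective size m = n × 3/π, m − 1 degrees of freedom and noncentrality d√m.

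- n = 23, d = 0.63: m = 21.96, noncentrality 2.95, power 0.804 (0.803 in 50,000 simulated exact tests).
- n = 25, d = 0.60: m = 23.87, noncentrality 2.93, power 0.801 (simulated 0.807).

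Both reproduce, so the stated sample size is not at issue.

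**2. Whom the rule removes.** Let A be starting a new drug and B stopping MTX. Removal requires A and B.

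| Participant | Removed? | Gives data after next-line start? |
|---|---|---|
| A and B (new drug replaces MTX) | Yes | No |
| A, not B (new drug added to MTX) | No | Yes |

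The next-line objective covers everyone with A. In the no-SCFA group A is the defining plan, so under this rule B alone decides whether post-start data exist. The exit sample in Section 7.3.5 does not fill the gap: taken on leaving at the switch, it cannot show change after the new drug has acted.

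**3. Control-group numbers.** Inputs from the Brief Summary: up to 30 enrolled, at least 20 wanted. Tolerance is (30 − 20)/30 = 33.3%, from all causes. The share f whose MTX is replaced is not in the documents, so it is an assumption. With all 30 places filled, no other losses and independent participants, expected retained = 30(1 − f), and the chance of reaching 20 is P(X ≥ 20) for X ~ Binomial(30, 1 − f).

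| Assumed f | Expected kept of 30 | Chance of at least 20 |
|---|---|---|
| 20% | 24 | 0.97 |
| 30% | 21 | 0.73 |
| 40% | 18 | 0.29 |
| 50% | 15 | 0.05 |

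**4. SCFA group before Visit 2.** The window is Days 15 to 45. Taking 65 as the cap on both groups together, the room for loss depends on how many control places are filled:

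- 30 controls: 65 − 30 = 35 SCFA places; 35 − 25 = 10 losses tolerable (29%).
- 20 controls: 65 − 20 = 45 SCFA places; 45 − 25 = 20 losses tolerable (44%), although the control target then has no slack.

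With 35 places, the chance of at least 25 evaluable is 0.93, 0.51 or 0.11 at an assumed pre-Visit 2 loss of 20%, 30% or 40%. At d = 0.60, power is 0.765 with 23 pairs and 0.699 with 20.

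**5. Selection at Visit 2, illustration only.** Assume no true change, 25 retained, loss share L, and correlation ρ between staying and diversity change. With c = z(L) and h = φ(c)/(1 − L), the spurious effect is d = ρh/√(1 − ρ²h(h − c)).

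| ρ | L | Spurious d | Two-sided rejection |
|---|---|---|---|
| 0.1 | 10% | 0.02 | 5.1% |
| 0.3 | 20% | 0.11 | 7.9% |
| 0.5 | 30% | 0.27 | 24% |

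Neither ρ nor L is given in the documents, so this range runs from negligible to material and settles nothing by itself.

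**The case against.** Much of the case on the other side stands.

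- **The control group is not emptied.** A reader might infer that it is, but removal needs a new drug and an MTX stop together, so add-on patients stay.
- **This is a secondary part of a pilot.** Section 9.1 says that adding controls leaves the primary analysis as it was. The next-line objective appears in the synopsis but not in Section 3.2. Visit 4 is optional, and only the synopsis ties it to next-line therapy; Sections 7.3 and 7.3.4 set no such condition.
- **The rule may be deliberate for the SCFA group.** The hypothesis is butyrate given with MTX, so ending participation when MTX stops fits it. That purpose does not extend to people who never take the supplement, and the text does not confine the rule to those who do.
- **Section 5.9 is not a contradiction.** A reader might set against the rule the statement that people who stop the compound "will be encouraged to remain on the study (not be officially withdrawn from the study) and complete all study visits". That covers stopping the supplement, a different event from replacing MTX, and the two rules can coexist.
- **Damage to the primary result is not shown.** No switching rate before Visit 2 is given. A willing participant removed at Day 15 or later could give an exit stool sample inside the Visit 2 window, though no text says it counts as Visit 2.
- **Ten tolerable SCFA losses is one allocation only.** It assumes every control place is filled; with 20 controls the figure is 20.
- **Keeping switched pairs in the main analysis has its own risk.** In a before-after comparison, a microbiome effect of the new drug would be credited to SCFA. Neither handling is clearly better, so I do not say which should be primary.

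None of this removes the conflict between Section 7.1.2 and the control-group and next-line text.

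**Conclusion.** The concern holds as a conflict within the document. As written, Section 7.1.2 limits next-line microbiome data to participants who stay on MTX, whereas the control-group definition, the synopsis objective, Section 9.1 and the stated purpose of the late visit carry no such limit. These places must be reconciled.

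The size is unknown because the documents give no MTX replacement rate. The firm statement is that the control target of 20 survives at most one third lost from all causes with 30 enrolled. The retention probabilities rest on assumed shares and independence.

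For the primary endpoint, the finding is only that handling is unspecified for SCFA participants switched off MTX before Visit 2. The effect is of unknown size and partly mitigated by the voluntary exit sample. The documents support neither a claim of demonstrated bias in the primary result nor one of an underpowered design.

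**What to change.** 1. **Scope of the rule.** Amend Section 7.1.2 to say that it does not end follow-up or sampling for the no-SCFA group or for Visit 4, and align it with the synopsis and Sections 5.4 and 9.1.
2. **Next-line analyses.** Derive two variables from the medication record: the start date of next-line therapy, and whether MTX was kept or replaced. Report microbiome change by both. Time since start matters because Visit 4 spans 421 − 61 = 360 days.
3. **SCFA participants whose MTX is stopped before Visit 2.** Keep collecting the scheduled samples if the participant is willing. Report the Visit 1 to Visit 2 change both with and without pairs collected after the switch, and state whether an exit stool sample inside the window may serve as Visit 2.

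The cost is a short amendment, some further sample visits and two derived variables. Medications are already reviewed at every visit and recorded under Section 7.4, so little new data collection is needed. The small downside is a more mixed treatment background in the follow-up data, which reporting by MTX status makes visible. Nothing here changes or proposes a treatment decision; it concerns only who stays under observation and how the data are reported.
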